3.5 Randomisation and Blinding

CHARIOT is not a randomised trial and is open labelled.

3.6 Sample Size

Sample size estimates are based on 1,000 simulated TiTE-CRM trials using the same characteristics that the actual trial will be based upon. The patients will not be replaced and the TiTE-CRM will use all accumulated data. For Stage A1, to treat 10 patients at a particular treatment plan or reach a maximum of 20 patients, 18 (95% C.I.: (10, 20)) patients are required. For Stage A2, to treat 6 patients at dosing schedule 4 or reach a maximum of 20 patients, 16 (95% C.I.: (11, 20)) are required.

3.7 Statistical Interim Analysis, Data Review and Stopping guidelines

This is a schedule finding trial and each time a patient is recruited, an interim analysis of the currently collected data will be performed to recommend the schedule of the newly recruited patient. See Section 3.1 for details.

3.8 Timing of Final Analysis

Based upon projected accrual rates, this trial (Stage A1, A2 and B) is expected to complete recruitment within 30 months of opening to recruitment. Final analysis for Stage A will be after all patients have been followed up for at least 3 months in Stage A1 and 26 weeks in Stage A2 while for Stage B, it will be performed 24 weeks after Stage B last patient start of treatment.

3.9 Blinded analysis

No blinded analysis will be undertaken for this trial as the trial is not randomised and therefore blinded.

3.10 Statistical Analysis Outline

Please refer to Section 3.1.

4. TREATMENT INTERVENTIONS

The trial is investigating the unlicensed drug M6620 in combination with the radiotherapy (stage A1); M6620 in combination with chemotherapy agents Cisplatin and Capecitabine (stage A2) and M6620 with chemoradiotherapy (stage B). For the purposes of the trial, M6620, Cisplatin and Capecitabine are all considered IMPs.

4.1 Stage A1 Treatment

Two M6620 dose levels and 3 dosing frequencies (treatment schedules) are proposed. Both the dose and frequency of M6620 will vary but the administered radiation dose and fractionation schedule will remain unchanged across treatment plans. The treatment schedule will last for 3 weeks and radiotherapy must start on a Monday.

4.1.1 M6620 treatment schedules – Stage A1

The starting dose of M6620 will be 140mg/m² IV once weekly (schedule 1). If schedule 1 is too toxic, the trial will be re-started at 90mg/m² (schedule -3). For all schedules, see Table 2. The treatment schedule of M6620 will be escalated or de-escalated using the TiTE-CRM model.

A phase I dose escalation safety study combining the ATR inhibitor VX-970 with chemoradiotherapy in oesophageal cancer using time to event continual reassessment method (funded by CRUK and Merck)
 EudraCT Number: 2015-003965-27

Table 2: Stage A1 - Dose Escalation Schedule

Dose Escalation schedule	
Treatment schedule	Dose** of M6620 and days of the schedule it will be delivered
-3	90 mg/m ² day 2, 9, 16
-2	90 mg/m ² day 2, 5, 9, 12, 16
-1	90 mg/m ² day 2, 5, 9, 12, 16, 19
1*	140 mg/m ² day 2, 9, 16
2	140 mg/m ² day 2, 5, 9, 12, 16
3	140 mg/m ² day 2, 5, 9, 12, 16, 19
4	240 mg/m ² day 2, 9, 16
5	240 mg/m ² day 2, 5, 9, 12, 16
6	240 mg/m ² day 2, 5, 9, 12, 16, 19

*Starting dose and schedule. 90mg/m² dose will only be explored if trial is re-started

**Doses are stated as exact dose in units. No intermediate dose levels or further splitting of the dose allowed

4.2 Stage A2 Treatment

Two dose levels and 2 dosing frequencies (treatment schedules) are proposed. Both the dose and frequency of M6620 will vary but the Cisplatin and Capecitabine dose and schedule will remain unchanged across treatment plans. The treatment schedule will last for 6 cycles (18 weeks).

4.2.1 M6620 Treatment Schedule – Stage A2

The starting dose of M6620 will be 90mg/m² IV once weekly (schedule 1). For all schedules, see Table 3. The treatment schedule of M6620 will be escalated or de-escalated using the TiTE-CRM model.

Table 3: Stage A2 - Dose Escalation Schedule

Dose Escalation schedule	
Treatment schedule	Dose of M6620 and days of the schedule it will be delivered
1	90 mg/m ² once a week for 18 weeks (Tuesdays)
2	90 mg/m ² twice a week for 18 weeks (Tuesdays and Fridays)
3	140 mg/m ² once a week for 18 weeks (Tuesdays)
4	140 mg/m ² twice a week for 18 weeks (Tuesdays and Fridays)

*Doses are stated as exact dose in units. No intermediate dose levels or further splitting of the dose allowed

A phase I dose escalation safety study combining the ATR inhibitor VX-970 with chemoradiotherapy in oesophageal cancer using time to event continual reassessment method (funded by CRUK and Merck)
 EudraCT Number: 2015-003965-27

4.3 Stage B Treatment

The dose administered in stage B will be 140mg/m² and will remain constant whilst three dosing schedules are explored. The chemotherapy and radiation doses and fractionation schedules will remain unchanged across dosing schedules.

The 11 weeks of treatment consists of 6 weeks of induction chemotherapy (Capecitabine and Cisplatin) with M6620 (Berzosertib) followed by 5 weeks of concomitant chemoradiotherapy (Capecitabine, Cisplatin and radiotherapy) with M6620 (Berzosertib). All patients will receive M6620 (Berzosertib) with induction chemotherapy on Cycle 1 Day 2 and Cycle 2 Day 2. In the last week of chemotherapy patients will be assigned to a M6620 (Berzosertib) treatment schedule to be administered during chemoradiotherapy. Radiotherapy must start on a Monday.

4.3.1 M6620 Treatment Dose and Schedule – Stage B

The dose of M6620 in Stage B will be confirmed prior to recruitment to stage B and the starting schedule will be treatment schedule 1.

Table 4: Stage B - Dose Escalation Schedule

Dose Escalation Schedule		
Treatment Schedule	M6620 administration during induction chemotherapy	M6620 administration during Chemoradiotherapy
-1	Cycle 1 day 2, Cycle 2 day 2	Days 9, 16, 23, 30
1	As above	Days 2, 5, 9, 16, 23, 26, 30
2	As above	Days 2, 5, 9, 12, 16, 19, 23, 26, 30, 33

5. STATISTICAL PRINCIPLES

5.1 Statistical Significance and Multiple Testing

There will be no statistical significance level defined for CHARIOT as it is a dose-finding trial and schedule recommendations will be based on the posterior probabilities calculated by the dose-toxicity model using all available data at each time.

5.2 Definition of Analysis Populations

Patients will not be replaced since TiTE-CRM uses all accumulated data and all patients will be evaluable for dose escalation decisions. However, the TMG may decide to replace patients if drop-out occurs early in the treatment schedule for reasons other than a DLT.

All patients who receive treatment within the study will be evaluable for response. All participants who receive at least one dose of M6620 will be evaluable for the safety analysis and included in the TiTE-CRM.

Evaluable for Objective Response: Only those patients who have measurable disease present at baseline, have received at least one cycle of therapy, and have had their disease re-evaluated will be considered evaluable for response. These patients will have their response classified according to the definitions stated

A phase I dose escalation safety study combining the ATR inhibitor VX-970 with chemoradiotherapy in oesophageal cancer using time to event continual reassessment method (funded by CRUK and Merck)
EudraCT Number: 2015-003965-27

in Protocol Appendix B (RECIST criteria). (Patients who exhibit objective disease progression prior to the end of cycle 1 will be considered evaluable.)

Evaluable Non-Target Disease Response: Patients who have lesions present at baseline that are evaluable but do not meet the definitions of measurable disease, have received at least one cycle of therapy, and have had their disease re-evaluated will be considered evaluable for non-target disease. The response assessment is based on the presence, absence, or unequivocal progression of the lesions.

[figure not shown]

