9. Haematological and biochemical indices within the ranges shown below:

Lab Test	Value required
Haemoglobin (Hb)	$\geq 10.0 \text{ g/dL}$
Platelet count	$\geq 100 \times 10^9/\text{L}$
Absolute neutrophil count (ANC)	$\geq 1.5 \times 10^9/\text{L}$
Total bilirubin	$\leq 1.5 \times \text{upper limit of normal unless the subject has known or suspected Gilbert's syndrome}$
AST (SGOT)/ALT (SGPT)	$\leq 2.5 \times \text{upper limit of normal or } \leq 5 \times \text{ULN in presence of liver metastases}$
Ca, Mg, Phosphate	Normal limits
Estimated glomerular filtration rate	$\geq 60 \text{ mL/min}$

Stage B

1. Histologically confirmed adenocarcinoma or squamous cell carcinoma of the oesophagus including Siewert type 1 or 2 tumours with $\leq 2 \text{ cm}$ gastric mucosal extension (not including cervical oesophagus).
2. Tumour length 7cm or less.
3. Suitable for radical CRT and surgery not an option due to being medically unfit or unsuitable for surgery or patient choice.
4. No oesophageal stent in situ.
5. Endoscopically or radiologically documented measureable disease.
6. Diagnostic PET CT scan*
7. Staging CT scan*

*either CT or PET CT within 42 days of first study dose
8. Adequate respiratory and cardiac function tests for safe delivery of CRT in the opinion of the Principal Investigator, specifically cardiac ejection fraction $\geq 60\%$ and lung function FEV1 $> 1 \text{ litre}$ or 40% of predicted value or KCO (DLCO/VA) $> 40\%$ predicted value.
9. Any gender, age ≥ 16 years.
10. ECOG performance score of 0-1.
11. Able to comply with protocol fully - absence of any physical, psychological, familial, sociological or geographical condition potentially hampering compliance with the study protocol and follow-up schedule; those conditions should be discussed with the patient before registration in the trial.
12. Able to give written (signed and dated) informed consent according to GCP before registration.
13. Haematological and biochemical indices within the ranges shown below:

Lab Test	Value required
Haemoglobin (Hb)	$\geq 10.0 \text{ g/dL}$
Platelet count	$\geq 100 \times 10^9/\text{L}$
Absolute neutrophil count (ANC)	$\geq 1.5 \times 10^9/\text{L}$
Total bilirubin	$\leq 1.5 \times \text{upper limit of normal unless the subject has known or suspected Gilbert's syndrome}$
AST (SGOT)/ALT (SGPT)	$\leq 2.5 \times \text{upper limit of normal}$
Ca (corrected), Mg, Phosphate	Normal limits
Estimated glomerular filtration rate	$\geq 60 \text{ mL/min}$

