6.3 Patient evaluability and replacement

Patients will not be replaced since TiTE-CRM uses accumulated data and all patients will be evaluable for dose escalation decisions. However, the TMG may decide to replace patients if drop-out occurs early in the treatment schedule for reasons other than a DLT.

In Stage B, all patients who receive treatment within the study will be evaluable for response. All participants who receive one dose of M6620 (Berzosertib) will be evaluable for the safety analysis.

Evaluable for Objective Response. Only those patients who have measurable disease present at baseline, have received at least one cycle of therapy, and have had their disease re-evaluated will be considered evaluable for response. These patients will have their response classified according to the definitions stated in Appendix B. (Patients who exhibit objective disease progression prior to the end of cycle 1 will be considered evaluable.)

Evaluable Non-Target Disease Response. Patients who have lesions present at baseline that are evaluable but do not meet the definitions of measurable disease, have received at least one cycle of therapy, and have had their disease re-evaluated will be considered evaluable for non-target disease. The response assessment is based on the presence, absence, or unequivocal progression of the lesions.

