
Note: Patients with a global deterioration of health status requiring discontinuation of treatment without objective evidence of disease progression [or evidence of unequivocal disease progression] at that time should be reported as "symptomatic deterioration". This is a reason for stopping therapy, but is NOT objective PD. Every effort should be made to document the objective progression even after discontinuation of treatment.
				

Complete or partial responses may be claimed only if the criteria for each are met at a subsequent time point at least 4 weeks later. The best overall response can be interpreted from Table B2.

Table B2: Response assessment after subsequent scan

Response: First time point	Subsequent time point	BEST overall response	Also requires
CR	CR	CR	Normalization of tumour markers All tumour nodes < 10 mm
CR	PR	SD, PD or PR (see comment*)	
CR	SD	SD provided minimum criteria for SD duration met, otherwise, PD	
CR	PD	SD provided minimum criteria for SD duration met, otherwise, PD	
CR	NE	SD provided minimum criteria for SD duration met, otherwise NE	
PR	CR	PR	
PR	PR	PR	
PR	SD	SD	
PR	PD	SD provided minimum criteria for SD duration met, otherwise, PD	
PR	NE	SD provided minimum criteria for SD duration met, otherwise NE	
NE	NE	NE	

* may consider PR providing initial "CR" likely PR on subsequent review – then original CR should be corrected. Recurrence of lesion after true CR is PD.

B.2.1 Frequency of tumour re-evaluation

Participants will receive CT scans at baseline and at 24 weeks after the start of treatment as per standard treatment.

B.2.2 Date of progression

This is defined as the first day when the RECIST (version 1.1) criteria for PD are met.

B.3 Reporting of tumour response

All patients included in the study must be assessed for response to treatment, even if there is a major protocol treatment deviation or if they are ineligible, or not followed/re-evaluated. Each patient will be assigned one of the following categories: complete response, partial response, stable disease, progressive disease, early death from malignant disease, early death from toxicity, early death from other cause or unknown (not assessable, insufficient data).

Early death is defined as any death occurring before the first per protocol time point of tumour re-evaluation. The responsible investigator will decide if the cause of death is malignant disease, toxicity or other cause.

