7.2.2 Secondary Outcomes

Safety and Toxicity Profile of the M6620 (All Stages)

The number (proportion) of patients who have had an AE recorded should be reported by schedule group. The number (proportion) of patients who have experienced one, two, three or more AEs will also be provided by schedule group. It is intended that the number of AEs recorded, the number of AEs per grade and the outcome will be reported.

This analysis will be repeated twice: once using serious adverse events (SAEs) and once using serious adverse reactions (SARs). Note: SARs are SAEs that are recorded as being possibly, probably or definitely related to a component of treatment. For SARs, the treatment component the event was related to may also be described.

Details of any SUSARs will be reported in the statistical report; the schedule group for the affected patient will be indicated.

Dose limiting toxicities are classed as SAEs in CHARIOT and will be analysed as described above. Length of time for toxicities to resolve will also be summarised and presented as mean (SD) or median (IQR).

Proportion of patients completing planned dose (All Stages)

To determine the ability to deliver the M6620 with palliative radiotherapy (Stage A1) and palliative chemotherapy (Stage A2), the proportion of patients completing at least 75%, 90% and 100% of the planned dose will be tabulated by schedule group.

A phase I dose escalation safety study combining the ATR inhibitor VX-970 with chemoradiotherapy in oesophageal cancer using time to event continual reassessment method (funded by CRUK and Merck)
EudraCT Number: 2015-003965-27

To determine tolerance and ability to deliver M6620 in combination with standard definitive chemoradiotherapy in Stage B, the proportion of patients completing at least 80% of the planned chemotherapy dose and at least 20 fractions of radiotherapy will be tabulated by schedule group.

Efficacy of the combination (All Stages)

Objective tumour response will be classified according to the RECIST v1.1 criteria. The number and proportion of patients who achieve Complete Response (CR), Partial Response (PR), (Stable Disease) SD and Progressive Disease (PD) will be reported overall and by treatment schedule.

Overall survival (OS) will be presented by stage using Kaplan Meier graphs along with two-sided 95% confidence intervals. Median and quartile OS will also be presented together with their 2-sided 95% confidence intervals if applicable.

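### The documents give incompatible populations for objective response and do not say which governs; the restrictive one would raise the response rate by dropping patients who fail without re-imaging

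*SAP*

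**What the plan says.** Four places bear on who counts in the objective response rate.

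- **SAP 5.2** opens with an inclusive rule for every stage: "All patients who receive treatment within the study will be evaluable for response". The definition that follows is restrictive: "Only those patients who have measurable disease present at baseline, have received at least one cycle of therapy, and have had their disease re-evaluated". It has one exception: "Patients who exhibit objective disease progression prior to the end of cycle 1 will be considered evaluable". Patients with only non-measurable lesions go to a separate non-target population, which also requires one cycle and a re-evaluation.
- **Protocol 6.3** carries the same pair, but its inclusive rule covers one stage only: "In Stage B, all patients who receive treatment within the study will be evaluable for response". Its restrictive definition is not limited by stage.
- **Protocol Appendix B.3** is broader than either: "All patients included in the study must be assessed for response to treatment, even if there is a major protocol treatment deviation". It extends this to patients who are ineligible or not re-evaluated, and provides categories for early death (by cause) and unknown.
- **SAP 7.2.2** gives the number and proportion with CR, PR, SD and PD, which "will be reported overall and by treatment schedule". It names no denominator and has no row for early death, unknown or non-CR/non-PD.

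Protocol 18 adds a general statement that all patients contribute to analysis whatever treatment or follow-up they complete.

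**The concern.** Two statisticians following these documents could report different response rates from the same data, and neither would be departing from the plan. The choice is not neutral. The restrictive rule requires a repeat assessment, and the patients most likely to lack one are those who died or became too ill to be scanned. They are treatment failures for this endpoint, and removing them raises the rate.

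Objective response is listed first among the efficacy endpoints in each stage (Protocol 3.1 and 3.2) and is tabulated by schedule, where groups are small and one or two exclusions are visible. If the denominator is left open until results are known, the choice may also appear to have been influenced by them.

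**Working it through.** The documents give no target response rate or response-based sample size, so there is no planned figure to reproduce. The check has two parts: who leaves under the restrictive rule, and what that does to the rate.

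**Who leaves**

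| Patient | Inclusive rule (SAP 5.2) | Restrictive rule | Appendix B.3 |
|---|---|---|---|
| Objective progression before end of cycle 1 | counted | counted (exception) | progressive disease |
| Dies before any re-imaging | counted | excluded | early death |
| Symptomatic deterioration, never re-imaged | counted | excluded | unknown, or early death if the patient dies before the first planned assessment |
| Non-measurable disease only, re-evaluated | counted | separate non-target population | category assigned |

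The third row is not rescued by the exception, because Appendix B says symptomatic deterioration is not objective progression. Protocol 14.10 foresees that investigators may stop imaging when progression is evident.

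**Direction.** Take N treated patients, r responders, and d patients excluded for lack of re-imaging. None of the d can be a documented responder. The rate moves from r/N to r/(N − d), which is larger whenever r ≥ 1 and d ≥ 1.

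**Non-measurable disease** behaves differently. Suppose 20 are treated, 4 have non-measurable disease, and 6 of the other 16 respond. The restricted rate is 6/16 = 37.5%. The all-treated rate is 6/20 = 30% with no CR among the 4, 7/20 = 35% with one, and 8/20 = 40% with two. The exclusion inflates the rate only if these patients respond less often than the rest.

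**How many might leave (illustration).** Inputs from the protocol:

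- median survival of 203 days with palliative radiotherapy and 25.4 months with standard chemoradiotherapy (section 1.1);
- response CT at week 12 in Stage A1 (5.4.1) and week 24 in Stage B (5.5.1);
- maximum sizes of 20 and 25 (synopsis).

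Under exponential survival, P(death before CT) = 1 − 0.5^(t/median):

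- A1: 1 − 0.5^(84/203) = 0.249, about 5 of 20. Inflation factor 1/(1 − 0.249) = 1.33.
- B: 25.4 × 30.4375 = 773 days; 1 − 0.5^(168/773) = 0.140, about 3.5 of 25. Inflation factor 1/(1 − 0.140) = 1.16.

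**Effect on the rate, with assumed responder counts:**

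| Setting | All treated | Restricted |
|---|---|---|
| N = 20, 6 responders, 2 dropped | 6/20 = 30.0% | 6/18 = 33.3% |
| N = 20, 6 responders, 4 dropped | 30.0% | 6/16 = 37.5% |
| N = 20, 6 responders, 5 dropped | 30.0% | 6/15 = 40.0% |
| N = 25, 10 responders, 3 dropped | 10/25 = 40.0% | 10/22 = 45.5% |
| N = 25, 10 responders, 4 dropped | 40.0% | 10/21 = 47.6% |

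Stage A2 images at weeks 6, 12 and 18 (Protocol 5.4.4), so fewer patients should leave before a first repeat scan.

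**The case against.** The strongest reply is that the documents do not show the restrictive rule governing. SAP 7.2.2 is silent, while Protocol 18 and Appendix B.3 favour inclusion. That stands: the defect is an unresolved conflict, and the bias is conditional on how it is resolved. A reader might infer that the plan will report an inflated rate; the text does not establish that.

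Several points also limit the size.

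- Objective progression before the end of cycle 1 is kept.
- Protocol 5.4.1 contemplates CT-identified progression before week 12, and Protocol 13.1 allows extra assessments when clinically indicated. Some deteriorating A1 patients would therefore be imaged and counted.
- Stage A1 entry requires ECOG 0-1 and a life expectancy of at least 12 weeks, so constant hazard from day 1 overstates early deaths.
- Protocol 18.1 records the number not evaluable, and the note closing the SAP's secondary outcomes asks for the number used in each analysis model. The denominator would be partly visible.

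Two further inferences are tempting and not supported. One is that Stage B enrols patients whom its endpoint excludes, because entry accepts "Endoscopically or radiologically documented measureable disease". The criterion still demands measurable disease, CT and PET-CT are also required, and the Stage B endpoint adds endoscopic and biopsy findings to RECIST. The other is that the one-cycle condition has no meaning in Stage A1. The protocol uses cycle language there, in the A1 DLT list (9.1.2) and the laboratory table (8.4), so the three-week course can be read as one cycle.

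Finally, SAP 1.2 says Stage B analysis methods will be added before that stage opens. That is an opportunity to settle the rule, but it does not resolve Stages A1 and A2.

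**Conclusion.** The point holds as a conflict with a known direction if resolved one way. The documents contain an all-treated rule, a restricted rule and an all-included rule for response, and none is given precedence. Applying the restricted rule removes patients who die or deteriorate symptomatically without re-imaging and raises the rate whenever anyone responds. No such certainty attaches to excluding non-measurable disease.

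The size is not derivable from the documents. The 25% (A1) and 14% (B) figures are upper-end illustrations. They rest on exponential survival, on medians from other trials, and on treating every death before the scheduled CT as un-imaged. The responder counts are assumed.

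The consequence is confined to a secondary, descriptive endpoint. SAP 5.1 sets no significance level, and the DLT endpoint, dose decisions and sample size do not depend on it. It should still be corrected, because it affects how a reader would judge activity and correction needs no new data.

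**What to change.** In SAP 5.2, SAP 7.2.2 and Protocol 6.3:

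1. Make the response-rate denominator all patients who received any study treatment (radiotherapy, chemotherapy or M6620), in every stage. The population with at least one M6620 dose, used for safety, is not a suitable substitute. M6620 starts on day 2 (Protocol 8.1.1, 8.2.3 and 8.3), so that population would lose patients who fail after day-1 radiotherapy or cisplatin.
2. Count patients without a repeat assessment as non-responders.
3. Add the Appendix B.3 early-death and unknown categories, and a non-CR/non-PD row, to the SAP 7.2.2 table.
4. Keep the measurable, re-evaluated subset as a labelled supportive analysis.

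The cost is wording in the SAP and a matching protocol amendment, agreed before response data are analysed. No new data are needed. The drawback is that the headline response rate may be lower.
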